7.2 Data Cleaning

Data cleaning of the behavioural data and fMRI data will be performed prior to unblinding. Cleaning of behavioural data (i.e. accuracy and reaction times) from the emotional processing tasks will be checked to ensure the tasks have been completed appropriately by

a clinical data analyst at P1vital Products. Specifically, trials where participants show unusually low response times (< 200ms) or high response times (> 6000ms) will be excluded. Similarly, participants who show abnormally low accuracy on the emotional tasks will be excluded (<50% correct responses on the FERT and FDOT). Cleaning of behavioural data from the non-emotional cognition tasks will be performed by the research team, coordinated by the Principal Investigator. Extreme outliers will be excluded from each group on a per task basis. The fMRI data cleaning will be performed by the research team, with guidance from BRC Imaging Support. fMRI data will be visually checked for excessive movement and other artefacts such as signal drop out, as well as to ensure all required data files are present. Formal MRI quality assessment will be undertaken using the MRIQC package (https://mrigc.readthedocs.io/en/stable/index.html), with data considered for rejection if falls outside the normal range of values in the derived image quality metrics. Following collection of all data to be analysed, a final data inclusion meeting will be held with the Principal Investigator prior to unblinding. This will review data quality and confirm exclusion of data from specific tasks. Data will be excluded on a per task basis—that is, a participant may have data excluded for one task, but have all other data available for analysis. Analyses of each task will then be performed on all randomised subjects who have data available for that task.

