Work in our group has revealed that short-term treatment with conventional antidepressants such as SSRIs produces positive biases in the processing of emotional information in healthy volunteers (5). For example, seven days treatment with the SSRI citalopram decreased recognition of negative facial expressions and recall of negative vs positive stimuli (6). There is also evidence showing that antidepressants have early effects on neural activity, acting on limbic-cortical brain regions that are known to be dysregulated in depression (7). Indeed, a key study by Godlewska and colleagues from our group showed that 7-day treatment with citalopram reduced activity in the anterior cingulate, insula, amygdala and thalamus in response to fearful versus happy facial expressions. Importantly, depressed patients with the greatest reduction in neural activity across these areas went on to respond better to SSRI treatment (8).

Such effects might be important neuropsychological mechanisms in the mediation of clinical antidepressant action and may also be useful as biomarkers to screen for potential antidepressant activity of novel compounds. It is currently unknown whether activating 5-HT4 receptors has similar effects on emotional

processing and neural activity. Such findings would be consistent with the animal studies and important further demonstration that 5-HT $_4$ receptor agonism might be a potentially useful avenue for antidepressant drug development. A previous study in our group revealed acute prucalopride administration (1mg) in 40 healthy volunteers potentiated learning and memory, whereby significantly more words were remembered in a test of auditory verbal learning and memory, and fewer false alarms were made in a delayed emotional recall task relative to placebo. A single dose of prucalopride did not, however, positively bias emotional processing.

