6.2 Objectives and Endpoints

These outcomes have been pre-registered on clinicaltrials.gov (NCT03572790). Primary outcomes are identified by bold typeface.

Objectives		Outcome measures / endpoints		
_	ate the effects of seven day e administration compared to			
Primary	Recognition of positive and negative facial expressions	Accuracy to recognise computer-based positive and negative facial expressions (anger, disgust, fear, happy, sad, surprise)		
		Misclassifications (number of responses to each facial expression category incorrectly classified as another facial expression category)		
		Reaction time to recognise facial expressions		
	Performance on Auditory Verbal Learning Task (AVLT)	Accuracy on AVLT (number of items correctly recalled across trials)		
		Number of intrusions (words incorrectly recalled) and number of repetitions (words repeated within the same trial)		
		Number of hits and false alarms in the delayed recognition test		
Secondary	Neural response to emotional faces	Blood Oxygen Level Dependent (BOLD) signal in areas including the amygdala, anterior cingulate cortex, and orbitofrontal cortex		
	Neural response to novel vs. repeated scenes	Blood Oxygen Level Dependent (BOLD) signal to scenes that have previously been seen compared to novel scenes in areas including the hippocampus and parahippocampal regions		
	Reward sensitivity as measured by the Probabilistic Instrumental Learning Task (PILT)	Amount won, amount lost, and total monetary amount earned Accuracy (correct or incorrect symbol choice) and proportion of group choosing correct symbol per trial		

Categorisation, recall, and recognition of emotional words on emotional memory	Emotional Categorisation Task (ECAT): accuracy and reaction time to classify positive and negative descriptor words
tasks	Emotional Recall Task (EREC): number of words correctly recalled (hits) and number of words incorrectly recalled (false alarms)
	Emotional Recognition Task (EMEM): accuracy and reaction time to correctly recognise positive and negative words (hits), and number of incorrectly recognised words (false alarms)
Vigilance to fearful and happy faces on the Facial Dot Probe Task (FDOT)	Vigilance scores derived from reaction time

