8.4.2.1 Primary outcomes

Facial Expression Recognition Task (FERT):

As in previous work (Harmer et al., 2004, Harmer et al., 2009), data will be analysed using repeated measures analyses of variance (ANOVAs). Group (prucalopride or placebo) will be the between-subject factor, and emotion (6 levels) will be the within-subject factor.

Auditory Verbal Learning Task (AVLT):

The number of correctly recalled words on the following trials will be calculated: List A immediate recall trials 1-5. A repeated measures ANOVA will be used to examine if there is an effect of prucalopride administration on word recall (between subject factor: group; within-subject factors: List A acquisition trial). Independent samples t-tests will be conducted to test if there is a group difference in the number of words accurately recalled after a short or long delay (List A short and long delay trials respectively, and the number of intrusions (incorrect words not present in list) and repetitions (correct words recalled more than once in the same acquisition trial) across List A acquisition trials. Independent samples t-tests will also be used to compare List B immediate recall and delayed recognition performance (number of hits and false alarms) between the groups.

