Task	Within Subject Factors	Number of Levels	Outcomes Used	Critical Contrasts Tested in the Analyses
FERT	Face Emotion	6 (Fear, anger, happy, surprise, disgust, sad)	% Accuracy Reaction time Misclassifications	Face emotion x treatment group
ECAT	Word Valence	2 (Positive, negative)	Accuracy Reaction time	Word Valence x treatment group
EREC	Word Valence Accuracy	2 (Positive, negative) 2 (Hits, false alarms)	Number of words recalled (correctly and incorrectly)	1. Word valence x treatment group 2. Word valence x accuracy x treatment group
EMEM	Word valence Accuracy	2 (Positive, negative) 2 (Hits, false alarms)	Number of words recognised (correctly and incorrectly) Reaction time	1. Word Valence x treatment group 2. Word valence x accuracy x treatment group
FDOT	Face Emotion Probe Duration	2 (Fearful, happy) 2 (Masked, unmasked)	Vigilance scores derived from reaction time	Face emotion x treatment group

				2. Face emotion x probe duration x treatment group
AVLT	/LT Trial 5 (List A acquisition tria 1-5)		Number of words recalled Number of intrusions Number of repetitions	Trial x treatment group
PILT	Trial type	2 (Win, loss)	1.Proportion of people choosing correct symbol	Trial type x treatment group
ОМТ	Trial 2 (1 probe, 3 probes)		 Proportion of correct probe selections Absolute error for probe location Reaction Time Proportion of misbinding errors 	1.Trial condition x treatment group

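### SAP 7.2 excludes participants below 50% correct on the FERT, so a primary analysis is selected on its own post-treatment outcome; the resulting bias is mainly towards the null

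*SAP*

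**What the plan says.** SAP 7.2 (Data Cleaning) sets the rule: "participants who show abnormally low accuracy on the emotional tasks will be excluded (<50% correct responses on the FERT and FDOT". It does not say whether the 50% is taken over all faces or within each emotion. The step is blinded: "Data cleaning of the behavioural data and fMRI data will be performed prior to unblinding", with a data inclusion meeting before the code is broken. It works task by task: "a participant may have data excluded for one task, but have all other data available for analysis".

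SAP 6.2 lists as a primary endpoint "Accuracy to recognise computer-based positive and negative facial expressions (anger, disgust, fear, happy, sad, surprise"; FERT misclassifications and reaction time are also primary, and the same exclusion filters them. SAP 4.5 bases the sample size on FERT accuracy for fearful faces. In the schedule (SAP 6.1) the FERT appears only at Visit 3, so there is no pre-treatment score.

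For the analysis, SAP 8.4.2.1 states that "emotion (6 levels) will be the within-subject factor", and the table of planned comparisons gives the critical contrast as "Face emotion x treatment group". Under SAP 8.4.2, a significant interaction is followed by independent t tests without Bonferroni correction. SAP 8.1 defines the non-fMRI population as everyone randomised except withdrawals and does not mention the accuracy exclusion. No analysis without the exclusion is planned.

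The Protocol synopsis predicts effects like those of serotonergic antidepressants, and Protocol section 4 describes these: "seven days treatment with the SSRI citalopram decreased recognition of negative facial expressions".

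**The concern.** A participant's FERT score on day 7 can be changed by the treatment. Dropping people because that score is low is a post-randomisation exclusion on the outcome itself, so the two groups that remain need not be comparable. Four of the six emotions (anger, disgust, fear, sadness) are negative. A drug that lowers their recognition also lowers overall accuracy and pushes more of the drug arm under the limit.

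The limit is also hard to justify as a check on effort. If the six listed expressions are the response options, guessing gives 1/6 = 16.7%, and someone at 45% is well above chance. The documents do not state the response options, so this is an inference. The FDOT differs: its endpoint is a vigilance score from reaction times, so an accuracy filter there does not cut the analysed score.

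At stake are the per-emotion differences for the first primary objective, the group main effect, and part of the 25 per group.

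**Working it through.** **The plan's own figure.** Protocol section 9 gives drug 10.64 (SD 9.77) and placebo 3.36 (SD 5.96), 25 per group, power 0.9. The difference is 7.28; the pooled SD is √((9.77² + 5.96²)/2) = 8.09; d = 0.90. Normal approximation, two-sided 0.05: 7.28/(8.09 × √(2/25)) = 3.18, and Φ(3.18 − 1.96) = 0.889, which agrees with 0.9 (an exact t calculation gives 0.876). That figure assumes all 25 per group are analysed.

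**Assumptions not in the documents.** Mean accuracy 55–70% on placebo; normal scores; equal SDs and equal correlations across emotions; the 50% limit applied to the six-emotion mean M; the drug lowers the four negative emotions by 7.28 points and leaves happy and surprise alone. Three variance settings are used:
- A: SD 15, correlation 0.3. Var(M) = 15² × (1 + 5 × 0.3)/6 = 93.75, so SD(M) = 9.68.
- B: between-person SD 8 plus emotion-specific SD 8.09. Var(M) = 64 + 8.09²/6, so SD(M) = 8.65.
- C: SD 8.09, correlation 0.3. Var(M) = 8.09² × 2.5/6, so SD(M) = 5.22.

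**Formulas.** With z = (mean of M − 50)/SD(M), the share excluded is Φ(−z). With equal SDs and correlations, Cov(each emotion, M) = Var(M). Keeping only M ≥ 50 therefore raises every emotion's mean by the same amount, SD(M) × φ(z)/Φ(z).

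**Worked case: setting A, mean 60%.**
- Drug-arm mean of M: 60 − 4 × 7.28/6 = 55.15.
- Placebo: z = 10/9.68 = 1.033; 15% excluded; means rise by 2.67.
- Drug: z = 5.15/9.68 = 0.532; 30% excluded; means rise by 4.77.
- Net distortion: 4.77 − 2.67 = +2.1 points on every emotion.
- Negative faces: −7.28 + 2.1 = −5.2. Happy: 0 + 2.1 = +2.1. Group main effect: −4.85 + 2.1 = about −2.7.
- Negative minus happy: −5.2 − 2.1 = −7.3, unchanged.
- Expected numbers left: 25 × 0.849 = 21.2 on placebo and 25 × 0.702 = 17.6 on drug.

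**Same formulas over the range** (excluded placebo v drug; remaining negative-face effect in points; spurious happy gain):

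| Mean | A | B | C |
|---|---|---|---|
| 55% | 30% v 49%; 4.5; 2.8 | 28% v 49%; 4.5; 2.7 | 17% v 49%; 4.8; 2.5 |
| 60% | 15% v 30%; 5.2; 2.1 | 12% v 28%; 5.3; 2.0 | 3% v 16%; 6.1; 1.2 |
| 65% | 6% v 15%; 5.9; 1.4 | 4% v 12%; 6.1; 1.2 | 0.2% v 3%; 7.0; 0.3 |
| 70% | 2% v 6%; 6.5; 0.7 | 1% v 4%; 6.7; 0.5 | under 0.1% v 0.2%; 7.2; 0.0 |

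If only fear falls by 7.28, M moves by 7.28/6 = 1.21. Setting A at 60% then excludes 15% v 18% and leaves 6.8 points. Setting C at 70% leaves about 7.3.

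**Simulation, 25 per arm.**
- No drug effect (B): type I error 0.047–0.052 for fear and 0.046–0.054 for negative versus positive.
- Power, t test on mean negative-face accuracy (A): about 0.68 to 0.47–0.49 at mean 60%, and 0.68 to 0.62 at 70%.
- Power, group by emotion test: about 0.4 to 0.3 (A, 60%), little changed at 70%; 0.93 to 0.91 (C, 60%).
- Happy faces, true effect zero, negative faces lowered (B): rejected in 5.1% (mean 70%) to 11.6% (mean 55%) of trials.
- Drug raises negative-face accuracy by 7.28 instead (B): also attenuated, to 5.2–7.0.

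**The case against.** The strongest defence is that the rule is prespecified, identical in both arms, applied per task and settled before unblinding. With no drug effect it removes both arms equally, and type I error stays at its nominal level. The planned critical contrast is the group by emotion interaction; because selection on the overall mean moves all emotions together, that contrast keeps its expected value and loses only sample size. All of this stands. It does not protect the follow-up t tests or the group main effect. The unbiasedness also rests on equal variances and correlations: with SDs of 12 for negative and 5 for positive faces, and a drug effect that lowers all six emotions equally, the negative-versus-positive contrast was rejected in 4.8–6.6% of simulated trials where it should be 5%.

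A second defence is size. The 7.28 points come from fearful faces only, and the Protocol prints the drug mean as the higher one, so neither the scale nor the sign establishes a 7.28-point fall in percent accuracy, let alone on four emotions. SD 15 is assumed. With SD 8.09, a fear-only effect or means of 65–70%, the distortion is much smaller. This also stands, and it is why the result is a range.

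Two stronger readings are tempting. A reader might infer that the rule manufactures false positive findings. It does not when the drug is inert; the spurious happy-face gain needs a real effect on other emotions and is small. A reader might also infer that the rule removes exactly those who show the hypothesised effect. It removes low scorers in both arms, more of them on drug if the drug works, and a fall in fear recognition alone need not take overall accuracy below 50%.

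**Conclusion.** The design fault is a matter of document fact: a primary outcome, measured only after treatment, decides who enters its own analysis, the population statement in SAP 8.1 does not reflect this, and no analysis without the rule is planned. SAP 7.2 does limit each task's analysis to participants with data for it, but that does not remove the selection.

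The main consequence, if the drug acts as predicted, is attenuation and lost power in the per-emotion comparisons and the group main effect. On the stated assumptions a 7.28-point effect is reduced by anything from almost nothing to (7.28 − 4.5)/7.28 = 38%. The size cannot be fixed more closely because the documents give no FERT accuracy distribution and do not say how the 50% is calculated. This should be fixed, but it does not by itself invalidate the planned interaction test.

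**What to change.** In SAP 7.2 and 8.1, define the primary FERT set as all randomised, non-withdrawn participants with FERT data. Exclude FERT data only for non-completion, for a prespecified share of trials outside the existing 200–6000 ms window, or for overall accuracy not distinguishable from guessing given the task's response options, which should be stated. Keep the 50% rule only as a sensitivity analysis, say whether it is overall or per emotion, and report the numbers excluded by arm. Leave the FDOT rule as it is. If unblinding has already taken place, label the change as made afterwards and report both analyses.

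The cost is SAP wording and one extra analysis. The downside is that a few poor performers stay in and may slightly raise the variance.

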7.3 Software

Behavioural Acquisition:

Qualtrics.XM (https://www.qualtrics.com) - screening and research visit questionnaires P1vital® Limited Products – Emotional Test Battery

Neurobehavioral Systems Presentation software (https://www.neurobs.com) - PILT, memory encoding task

Oxford Memory Test application "Short_Fractals1" – modified from "What was where task" (Pertzov et al., 2013) running on iOS 12.3.1

Behavioural Analysis:

IBM SPSS Statistics 25 or latest version Mathworks MATLAB_R2018a

MRI stimulus presentation: Psychopy version 1.84.2 (http://www.psychopy.org)
MRI physiological measurement acquisition: Biopac MP150 system, software level
3.0.0.4 (https://www.biopac.com), Eyelink ® (https://www.sr-research.com)
MRI analysis:

heudiconv 0.5.4 (https://github.com/nipy/heudiconv);

MRIQC (latest version available) (https://mriqc.readthedocs.io);

fmriprep (latest version available) (https://fmriprep.readthedocs.io);

FSL 6.0 or latest version available

(https://process.innovation.ox.ac.uk/software/p/9564/fslv5/1);

TEDANA (latest version available) (https://tedana.readthedocs.io);

BASIL (latest version available) (https://fsl.fmrib.ox.ac.uk/fsl/fslwiki/BASIL);

Quantiphyse (latest version available)

(https://process.innovation.ox.ac.uk/software/p/14419/quantiphyse-academic-workflow/1)

All final versions of software and computing environments will be fully documented for computational reproducibility of analysis.				

8. Statistical Analysis

8.1 Analysis Populations

The population used for the analysis of data in this study will be:

- All randomised subjects for non-fMRI data, except for withdrawn participants who will not be included in the analysis.
- As per protocol set for fMRI data (criteria: fMRI data available). fMRI data will not be available for all participants per se depending on need to exclude / withdrawal.

8.2 Handling missing data

Withdrawn participants' data will not be included in the analysis.

8.3 Measurements of treatment compliance

Participants were given a pill bottle containing 9 capsules of prucalopride or placebo: seven for daily administration over the study period, and two spare in case participants dropped or lost a capsule. Participants were sent daily text or email reminders to take their capsule. On day 7 (Research Visit 2), participants were asked their adherence to the seven day schedule. Participants were asked to return their pill bottle and the researchers recorded how many pills remained, along with any reasons for greater or fewer than two pills remaining.

8.4 Analysis of outcome parameters

Details of the study endpoints can be found in section 6. All key endpoints will be summarized (mean, standard deviation) in tables and bar charts (mean ±SEM).

8.4.1 Demographic data and psychometric data

To assess changes in subjective mood and anxiety before and after prucalopride/placebo administration, mixed model ANOVAs will be performed with time as a within-subjects factor and group as a between-subjects factor on STAI-S, PANAS, and VAS ratings. Post hoc analyses using independent samples t tests will follow up any significant interactions. A generalised linear model will be used to analyse side effects.

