6. STUDY PROCEDURES

Baseline Assessments and Procedures

Individuals who are interested in participating in the study will be invited to attend a Screening Visit (maximum 2 hours). Demographic information will be collected:

Age (years, months), years in full-time education

Participants' eligibility to take part will be checked by recording the following:

- Weight, height, and BMI
- Number of cigarettes smoked per day, units of alcohol consumed per week, caffeinated drinks consumed per day
- Medical history (including family psychiatric history), details of current and past medication
- Current and prior use of drugs (to exclude for drug use in the three months prior to the study)
- Menstrual cycle (in order to avoid scheduling testing in the premenstrual week)
- SCID-V interview (Structured Clinical Interview for DSM-V) to probe for current or past psychiatric illness
- Urine pregnancy test (female participants only)
- MRI screening form to ensure no contraindication to MRI scanning
- Edinburgh Handedness Inventory (see APPENDIX G: STUDY QUESTIONNAIRES)

The following baseline assessments will be completed (APPENDIX G):

- Beck Depression Inventory (BDI)
- Eysenck Personality Questionnaire (EPQ)
- State and Trait Anxiety Inventory (STAI)
- Positive and Negative Affect Schedule (PANAS)
- Snaith-Hamilton Pleasure Scale (SHAPS) a measure of anhedonia
- National Adult Reading Test (NART) a measure of verbal intelligence
- Side effect questionnaire (to determine baseline of bodily symptoms/'side effects')
- Visual Analogue Scales (VAS) measuring subjective state

Participants will be asked to wait while their eligibility to take part is assessed by a medical doctor involved in the study (maximum 30 minutes). Any participant for whom additional information is required before an eligibility judgment can be made will be asked to return on a different day once this information has been obtained.

Eligible participants will be randomised, using an online randomisation tool, to receive either seven-day prucalopride, or seven-day placebo administration. Randomisation will occur on the day of screening, or up to a maximum of four weeks after screening. Randomisation after the screening visit will occur in the event that further information is needed before determining whether participants are eligible to take part (for example, if a participant needs to follow up with details of allergies, or previous studies they have taken part in). In this

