4.1 Summary of study design

This is a double-blind placebo-controlled parallel group experimental medicine study, which will be conducted at the University of Oxford, Department of Psychiatry. The site will recruit 50 healthy volunteers between the ages of 18 and 40. Study staff will identify potentially eligible participants from the general public, who will be made aware of the trial through advertisements on local information websites (e.g. Daily Info, Oxford University Gazette), newspapers, local magazines, on the radio and on the lab webpage, Facebook page and Twitter account, and in universities and other public places. Each participant will attend 3 study visits in total which will be conducted at the Department of Psychiatry. After having confirmed initial study eligibility by phone or email (Pre-Screening), participants will be invited to the department for the Screening Visit (2 hours). If this visit qualifies them as eligible, participants will be recruited into the study and will be invited for visits 2 and 3 on two consecutive days, no later than 1 month after the Screening Visit. Visit 2 will be the Research Visit 1 (~1.5 hours), and visit 3 will be the Research Visit 2 (~3 hours), where behavioural and neural parameters will be obtained. Self-report clinical symptom severity (mood, anxiety and side effects) will be measured on all visits, and before and after testing on visit 2 and visit 3.

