4.3 Methods of assigning subjects to treatment groups

Eligible participants will be randomised to receive either seven-day prucalopride, or seven-day placebo administration. Randomisation will occur on the day of screening, or up to a maximum of four weeks after screening.

The randomization code will be drawn up by a researcher not involved in the study using an online randomization tool (www.sealedenvelope.com). Randomisation will be stratified for gender and blocked with a block size of 4.

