4.5 Determination of Sample Size

We will be using the Emotional Test Battery, which is a well validated set of emotional processing tasks that are sensitive to antidepressant effects. On the facial expression recognition task (FERT), one of the main outcome variables is accuracy at recognising fearful facial expressions and this is the variable used for power calculations. Based on data acquired in (Harmer et al., 2004) comparing citalopram to placebo, if we aim for 0.9 power and a 0.05 false positive rate, a suggested total sample size is 38 (G*power) to ensure determination of group level differences at this variable if they exist. As 5HT₄ agonism is less well studied and the dose required of prucalopride for optimal agonism at the receptor is uncertain, we will aim for 25 individuals per group (total sample size of 50).

5. Changes in the Conduct of the Study or Planned Analyses

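### Mood and anxiety scales are tested only by a time x group ANOVA with undefined time levels and no screening covariate, which is inefficient for a sustained drug effect

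*SAP*

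**What the plan says.** SAP 8.4.1 gives the purpose as "To assess changes in subjective mood and anxiety before and after prucalopride/placebo administration". The method, for STAI-S, PANAS and VAS, is that "mixed model ANOVAs will be performed with time as a within-subjects factor and group as a between-subjects factor". The only further step is "Post hoc analyses using independent samples t tests will follow up any significant interactions". No covariate is named. The section does not give the number of time levels, and it does not say whether the group main effect will also be read. Protocol section 9 likewise plans repeated-measures ANOVA for mood and anxiety.

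The occasions have to be taken from elsewhere. SAP 4.1 says that self-reported symptoms "will be measured on all visits, and before and after testing on visit 2 and visit 3", and the schedule in SAP 6.1 agrees. Protocol section 6 lists STAI, PANAS and VAS among the baseline assessments at screening, before any capsules are handed out. There is therefore one pre-treatment value and four on-treatment values, the latter on days 6 and 7. On the interval before treatment, SAP 4.3 says "Randomisation will occur on the day of screening, or up to a maximum of four weeks after screening".

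SAP 6.2 does not list these scales among its objectives and endpoints.

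**The concern.** If all five scheduled occasions enter the ANOVA, a drug effect present throughout days 6 and 7 has a simple shape: no difference at screening, then the same difference four times. The interaction test spreads its sensitivity over every possible pattern across five occasions (4 degrees of freedom), although this pattern needs only one. The group main effect does not fill the gap, because it averages in the screening occasion, where randomised arms differ only by chance. The follow-up comparisons depend on the interaction being significant, and they make no use of the screening value.

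At stake is how far a null result on mood and anxiety can be trusted with 25 per arm. A non-significant interaction could be read as no effect on mood when the test had limited power for the most straightforward kind of effect.

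**Working it through.** **The plan's own figure.** There is none for these scales. The only power figure, 0.9, concerns fear accuracy on the facial expression task. The documents give no effect size, SD or correlation for mood or anxiety, so those below are assumptions shown over a range.

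**Inputs.** n = 25 per arm (SAP 4.5), two-sided 5%, SD 1 at each occasion, no dropout (withdrawn participants are replaced, protocol section 6). Five occasions are inferred from SAP 4.1 and 6.1. The assumed effect d is 0.6 SD at all four on-treatment occasions. Let r be the correlation between occasions. Where needed, r0 is the correlation with screening and r1 the correlation among on-treatment values.

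**Noncentrality (λ), sustained effect**
- Interaction: λ = (n/2) x Σ(δ_t − mean δ)² / (1 − r). With δ = (0, d, d, d, d) the mean is 0.8d and the sum is 0.64d² + 4 x 0.04d² = 0.8d². So λ = 12.5 x 0.8 x 0.36 / (1 − r) = 3.6 / (1 − r), on 4 and 192 df.
- Unadjusted on-treatment mean: variance V = (1 + 3r1)/4, so λ = 12.5 x 0.36 / V = 4.5 / V, on 1 and 48 df.
- On-treatment mean adjusted for screening: λ = 4.5 / (V − r0²), on 1 and 47 df.

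| r | Interaction λ, power | Unadjusted mean λ, power | Adjusted mean λ, power |
|---|---|---|---|
| 0.4 | 6.0, 0.46 | 8.2, 0.80 | 11.5, 0.91 |
| 0.5 | 7.2, 0.54 | 7.2, 0.75 | 12.0, 0.92 |
| 0.6 | 9.0, 0.65 | 6.4, 0.70 | 13.2, 0.95 |
| 0.7 | 12.0, 0.79 | 5.8, 0.66 | 15.8, 0.97 |

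Simulation with the Greenhouse-Geisser correction (stated in SAP 8.4.2 for behavioural data and assumed to apply here) agrees within about 2 points: 0.44 to 0.78 for the interaction and 0.90 to 0.97 for the adjusted mean. Type I error is about 4 to 5% for both. The five-occasion group main effect has λ = 12.5 x 0.64 x 0.36 / ((1 + 4r)/5), and its power falls from 0.64 at r = 0.4 to 0.48 at r = 0.7.

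**Where the gain comes from.** At r = 0.5 the interaction and the unadjusted mean have the same λ of 7.2. Going from 4 df to 1 raises power from 0.54 to 0.75, and the covariate raises it further to 0.92. That is about 21 points from averaging and 17 from adjustment. At r = 0.7 averaging without the covariate is worse than the planned test (0.66 against 0.79), so the covariate is essential there.

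**Weaker correlation with screening**
- r0 = 0.3, r1 = 0.7: V − r0² = 0.775 − 0.09 = 0.685, λ = 6.6, power 0.71 (simulated 0.70), against a simulated 0.45 for the interaction. Without the covariate the mean already reaches 0.66.
- r0 = 0.5, r1 = 0.8: 0.85 − 0.25 = 0.60, λ = 7.5, power 0.76, against a simulated 0.60.

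**Two time levels only** (screening and one on-treatment value). Interaction λ = 12.5d² / (2(1 − r)); adjusted λ = 12.5d² / (1 − r²). At d = 0.6, simulated power is 0.55 against 0.66 (r = 0.5) and 0.77 against 0.82 (r = 0.7). At d = 0.5 the gain is about 3 to 14 points for r from 0.8 down to 0.3.

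**Effect not sustained** (0.8 SD on day 7 only, r = 0.5)
- Five-level interaction: Σ = 3 x 0.16d² + 2 x 0.36d² = 1.2d², λ = 12.5 x 1.2 x 0.64 / 0.5 = 19.2, power 0.95.
- Adjusted mean: the average effect is 0.4, λ = 12.5 x 0.16 / 0.375 = 5.3, power 0.62.
- Group x occasion over the four on-treatment values: Σ = 4 x 0.25d² = d², λ = 12.5 x 0.64 / 0.5 = 16, 3 df, power 0.93 (simulated 0.91 to 0.93).

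**The case against.** The planned test is valid. Time x group asks directly whether change differs between arms, which is the stated aim, and it keeps its error rate. It also matches the protocol. The issue is therefore efficiency, and that part of the objection stands.

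Three stronger readings are tempting, and the documents do not support them.

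- A reader might infer that the SAP treats screening as one of five time levels. SAP 8.4.1 does not define the factor; five is the number of scheduled occasions. What can be said is that the factor is undefined and that the size of the loss depends on its definition.
- A reader might infer that baseline adjustment is markedly better at no cost. Equal correlation flatters it: screening may precede randomisation by up to four weeks, while the four later values fall on two consecutive days. Much of the gain can come from averaging. Averaging alone also loses clearly when the effect is confined to one day or to one side of the task session. Because the scales are taken on both sides of each session, such patterns are plausible. This objection is met only if the group x occasion test is kept.
- A reader might infer that the task findings are put at risk because these scales serve to rule out mood as an explanation. Neither document gives them that role, and no listed primary or secondary conclusion rests on them.

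**Conclusion.** The point holds as a matter of efficiency and specification. A pre-treatment value is collected for every scale and is not planned as a covariate, the time factor is undefined, and group comparisons are reached only through a significant interaction. If all five occasions enter and the effect is broadly sustained, the adjusted on-treatment mean gains roughly 19 to 46 points of power under equal correlation (0.78 to 0.97 at r = 0.7; 0.44 to 0.90 at r = 0.4). It gains roughly 16 to 25 points when screening correlates less with later values (0.60 to 0.76; 0.45 to 0.70). With two time levels the gain is modest. For effects confined to some occasions, the averaged test used alone is the weaker one.

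All of this rests on assumed effect sizes and correlations, because the documents give none for these scales. Importance is minor to moderate, since the scales are not listed endpoints.

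**What to change.** In SAP 8.4.1:

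1. State which occasions form the time factor.
2. For each of STAI-S, PANAS and VAS, model the four on-treatment values (repeated-measures ANCOVA or mixed model) with the screening value of the same scale as covariate.
3. Name the group effect averaged over the four occasions as the main test.
4. Pre-specify group x occasion (day 6 or 7, before or after the session) as the second test, and report it whatever the result of the first.
5. Report adjusted group differences with confidence intervals, so that a null result can be judged by its precision.

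The cost is one residual degree of freedom and two named tests instead of one, so their order must be fixed in advance. No new data are needed. If these scales have already been analysed, report the adjusted model as a labelled sensitivity analysis beside the planned ANOVA.
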